HPV31/33/35/39/45/51/52/53/56/58/59/66/68 for exploratory aims. Participants positive for high-risk HPV and/or HPV6/11 on any sample will have a 6-12 month follow-up visit to measure HPV type-specific persistence - a surrogate endpoint recommended by the WHO (87). At young ages, the risk of precancer is very low, but for safety purposes, participants will be offered colposcopy if they have a persistent high-risk HPV cervical infection and anoscopy if they have a persistent HPV16/18 anal infection. Main outcomes will be prevalence and 6-12 month type-specific persistence of cervicovaginal (as an excellent proxy for cervical sampling (87)), anal, and/or oral infections by HPV6/11/16/18 as well as antibody titers for HPV6/11/16/18. Cervical and anal biopsy specimens diagnosed as CIN2+ or AIN2+, respectively, will also be tested for the 15 high-risk and 2 low-risk HPV types for secondary outcomes. In an exploratory aim, we will examine risk factors, including the cervicovaginal microbiome (88), for HPV type-specific persistence in WLWH and HIV[-] women.

At enrollment, blood will be collected for plasma from all participants. In the study laboratory, a stratified random sample of specimens will be selected to measure by ELISA anti-HPV16 and -HPV18 antibody titers and compare HPV-vaccinated WLWH. We will test titers in at least 1,302 samples ($n \geq 548$, 50% with three doses and 50% with two doses of Gardasil®, for both HPV-vaccinated WLWH and for HPV-vaccinated HIV[-] women; $n \geq 108$ for both HPV-vaccinated WLWH and for HPV-vaccinated HIV[-] women as controls) and up to 3,028 samples.

VI.B. Study Locations

In Kigali, the study staff will work with five public clinics that participate in the International Epidemiology Databases to Evaluate AIDS (IeDEA) program and the WE-ACTx private clinic (**Table 2**). Study investigators and staff successfully worked with these clinics in a cervical cancer screening study of 5,000 WLWH (83). If needed, the staff will work with up to four other public health clinics to recruit additional participants.

Table 2. Study enrollment sites	
IeDEA Sites	Non-IeDEA sites
1. Busanza health center (HC)	1. Cor-unum HC

2. Gikondo HC 3. Kicukiro HC 4. Nyarugunga HC 5. Rwanda Military Hospital 6. WE-ACTx private clinic	2. Kacyiru HC 3. Remera HC 4. Rwampara HC
---	---

VI.C. Target Population

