A summary of the management of HPV-positive results is shown in **Figure 4**. To ensure the safety of participants, those who at the follow up visit, have a type-specific persistent HPV infection for one or more of the 15 hrHPV types (HPV16/18/31/33/35/39/45/51/52/53/56/58/59/66/68), regardless of HIV status, will be referred to colposcopy. Colposcopy and treatment will be performed at RMH by a trained study physician or gynecologist on staff at the hospital.

Digital images of the cervix will be taken using a study-provided contemporary digital camera (e.g., Samsung A21S or similar cellular phone camera). The participant's images will be shown to her if she so desires. All images from a participant will be identified using a study ID. Images will not be analyzed at the clinic visit but be stored in the study secure NIH server immediately or, if not possible at the time, images will be uploaded when secure access to the study server becomes available. Images will be used for later analyses with automated visual evaluation algorithms being developed at the NCI for management of HPV-positive women (90).

Biopsies will be taken of all acetowhite, visible cervical abnormalities consistent with the American Society for Colposcopy and Cervical Pathology (ASCCP) management guidelines (91). The colposcopy impression and location of biopsies will be recorded for clinical management files and saved in the participant record for study purposes.

[figure not shown]

Figure 4. Follow-up and Clinical Management of Baseline HPV-Positive Results

After undergoing colposcopy and biopsies, WLWH with persistent HPV16- or HPV18 infection will receive ablative treatment unless ineligible for ablative treatment per WHO Guidelines (92); those ineligible for ablation will receive treatment by LEEP. Biopsies will be read by two local pathologists and [name] (Einstein). All participants diagnosed with CIN3+ will undergo treatment. In accordance with ASCCP guidelines, those diagnosed with CIN2 will not undergo immediate treatment due to the low risk of ICC following a CIN2 diagnosis, especially in young women, and the possible increased risk in negative reproductive outcomes such as pre-term delivery following treatment (10). They will be advised to seek clinical follow-up in a year.

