After processing and reading according to local practices, formalin-fixed paraffin-embedded (FFPE) tissue specimens from biopsies and excisional treatment with results of CIN2+ will be sent to the study lab for HPV typing for study purposes (**Section VI.I.1.**).

To summarize, within the context of the research protocol, participants at risk of precancer will be provided with colposcopy as well as treatment and follow-up. Participants with a diagnosis that requires treatment beyond ablation or excision (i.e., invasive cervical cancer), will be referred and guided to appropriate local care.

VI.G.2. Management of Persistent Anal HPV

WLWH with persistent HPV16 or HPV18 infection will undergo anoscopy; HIV[-] participants with persistent HPV16- or HPV18 infection will not undergo anoscopy due to their still low absolute risk of anal cancer (10) and the morbidity of treating anal abnormalities. Anoscopy and treatment will be performed at RMH by a study physician on staff at the hospital with training for this protocol.

A biopsy will be taken from acetowhite lesions. The anoscopy impression and location of biopsies will be recorded for clinical management files and saved in the participant record for study purposes. After processing and reading according to local practices, formalin fixed, paraffin embedded (FFPE) tissue specimens from biopsies and excisional treatment with results of anal intraepithelial neoplasia (AIN) grade 2 (AIN2) or more severe diagnoses (AIN2+) will be sent to the study lab for HPV typing analysis (**Section VI.I.1.**).

Those with a biopsy diagnosis of AIN grade 3 (AIN3) or anal cancer will be treated or referred for anal cancer management, respectively. Those diagnosed with AIN2 will not undergo immediate treatment due to the low risk of anal cancer following a AIN2 diagnosis and the aforementioned morbidity associated with treatment. Those with untreated AIN2 or persistent anal hrHPV by non-HPV16/18 types will be advised to seek clinical follow-up in a year.

Similar to colposcopy, within the context of the research protocol, participants at high risk of anal precancer will be provided with anoscopy as well as treatment and follow-up. Participants with a diagnosis that requires treatment beyond routine care (i.e., invasive anal cancer) will be referred and guided to appropriate local care.

VI.G.3. Management of Persistent Oral HPV

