Similarly, exploratory analyses will compare the effectiveness of HPV vaccination for cross-protection types and endpoints of cumulative detection of Gardasil®-targeted HPV types-associated CIN2+ and/or anal intraepithelial neoplasia grade 2 or more severe (AIN2+) (vs. untargeted HPV type-associated CIN2+ and/or AIN2+) between study groups.

For participants in the existing IeDEA database we will extract HIV specific variables. For those who we cannot match to the IeDEA database, will extract HIV specific variables from medical records.

In another exploratory analysis, among WLWH, the presumed route of HIV acquisition (either maternal to child or behavioral) will be compared with HPV positivity and, among HPV-positive women, HPV viral load.

VII.A.2. Sample Size/Power for Gardasil®-vaccinated vs. unvaccinated WLWH.

For this analysis, we will make the following assumptions: 1) at least 30% prevalence of HPV infection (of any anatomic site) at baseline, 25% of which will be Gardasil®-target HPV types and 55% will be untargeted HPV types, 2) a 10% loss to follow-up (LTFU) in at follow up visit, and 3) at least 70% of HPV infections persist for 6-12 months. We justify an HPV prevalence of at least 30% based on 30% prevalence of high-risk HPV infection of the cervix in 30-year-old WLWH from our previous U54 study (109). We expect that the HPV prevalence may be higher since the prevalence of HPV, like that of other sexually transmitted infections, tends to peak about 5 years after the median age of sexual initiation in a population. However, we conservatively used 30% to ensure adequate statistical power. We justify our assumption of a maximum of 10% follow-up, given our experience working in Rwanda over the last ~20 years. We justify 70% of prevalent HPV infections persisting for 6-12 months, given that 36-50% of prevalent HPV infections persist 6-months in HIV[-] women (109, 110) and WLWH have an impaired immunity to HPV (8, 9).

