a blood draw for anti-HPV16 and HPV18 antibody titer testing. All participants will provide a cervicovaginal, anal, and oral specimens for high-risk HPV and HPV6 and HPV11 testing. Specifically, participants will provide an oral rinse sample collection by gargling and swishing a saline solution for 30 seconds before spitting the rinse into a specimen container. The study nurse will help the participant count time and provide the collection. Then, while lying on the exam table, the study nurse will collect a specimen taken vaginally (without the use of a speculum) using a cervical brush. The study nurse will then collect a sample from the anal canal using a scored, Dacron swab. In addition, participants not known to be HIV-infected will have a rapid HIV test with pre- and post-counseling.

We anticipate that approximately 30% of participants will test positive for high-risk HPV and/or HPV6/11 on any sample and be invited for a 6-12 month follow-up visit. At that visit, participants will provide only specimens from those anatomic sites that were HPV-positive at baseline to measure 6-12 month HPV type-specific persistence. For safety purposes, WLWH and HIV[-] women with a cervicovaginal type-specific persistent hrHPV infection will be referred to colposcopy, and WLWH with an anal type-specific persistent HPV16/18 infection will be referred to anoscopy (**Section VI.G**). At the colposcopy and anoscopy procedure and follow-up visits, participants will be treated as needed.

All participant data collected will be entered or transferred to a secure REDCap database, with access to personal information restricted to the local staff. Study data will be stored in REDCap and maintained on password protected study computers behind the institution firewall. REDCap is a secure, web-based application designed to support data capture for research studies providing: 1) an intuitive interface for validated data entry; 2) audit trails for tracking data manipulation and export procedures; 3) automated export procedures for seamless data downloads to common statistical packages; and 4) procedures for importing data from external sources.

Potential risks from these procedures include:

- *Eligibility Screening.* Potential participants will be asked to confirm their history of any sexual activity and that might make them feel uncomfortable. This question will be asked in a neutral manner in a private location.

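### Minor, exploratory endpoint: for vaccinated WLWH vs vaccinated HIV[-] women, adding AIN2+ to CIN2+ biases the targeted/untargeted ratio upward, because AIN2+ can be found only in WLWH with persistent anal HPV16/18

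*Combined protocol and SAP*

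**What the plan says.** **Endpoint.** VII.A.1 describes "cumulative detection of Gardasil®-targeted HPV types-associated CIN2+ and/or anal intraepithelial neoplasia grade 2 or more severe (AIN2" and contrasts it with untargeted-type CIN2+ and/or AIN2+ between study groups. The paragraph names no pairs of groups. It opens with *Similarly*, directly after the three infection ratios: Group 1 vs 2, Group 1 vs 3 and Group 3 vs 4. Nothing limits the lesion comparison to some of these.

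**Finding CIN2+.** VI.G.1 refers to colposcopy, whatever the HIV status, all women who "have a type-specific persistent HPV infection for one or more of the 15 hrHPV types".

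**Finding AIN2+.** VI.G.2 gives anoscopy to WLWH with persistent HPV16 or HPV18 and adds: "HIV[-] participants with persistent HPV16- or HPV18 infection will not undergo anoscopy". Women with "persistent anal hrHPV by non-HPV16/18 types will be advised to seek clinical follow-up in a year". X.A.2 agrees: "WLWH with an anal type-specific persistent HPV16/18 infection will be referred to anoscopy". VI.A is looser: "participants will be offered colposcopy if they have a persistent high-risk HPV cervical infection and anoscopy if they have a persistent HPV16/18 anal infection". It states no HIV restriction.

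**Tissue.** In VI.G.1, WLWH with persistent HPV16/18 are treated after biopsy, and "those ineligible for ablation will receive treatment by LEEP". Then "tissue specimens from biopsies and excisional treatment with results of CIN2+ will be sent to the study lab for HPV typing".

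**Status.** VII.A.1 calls the lesion comparison exploratory. VI.A and XI call these outcomes or analyses secondary. XI says the women are too young for many such events. It does not mention unequal ascertainment.

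**The concern.** The relative measure uses untargeted types as an internal control for exposure. That works only if targeted and untargeted lesions are looked for in the same way in both groups. For CIN2+, referral meets this condition. For AIN2+ it does not: one group is examined and the other is not, and entry to the examination is by targeted type. The untargeted denominator cannot correct a selection that is itself made by type.

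Group 1 vs 3 asks whether the vaccine works as well in WLWH as in HIV-negative women. A composite run on that pair could suggest poorer effectiveness in WLWH that comes only from who was examined.

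**Working it through.** The plan gives no event rate, sample size or power for this endpoint, so there is no figure to reproduce.

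**Step 1. Who can contribute a lesion (VI.G.1, VI.G.2, X.A.2).**

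| Groups | CIN2+ found after | AIN2+ found after |
|---|---|---|
| 1 and 2 (WLWH) | persistence of any of 15 types | anal HPV16/18 persistence only |
| 3 and 4 (HIV[-]) | persistence of any of 15 types | no study anoscopy |

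**Step 2. Direction.** Let Tc and Uc be targeted and untargeted CIN2+ counts, set equal in Groups 1 and 3 so that the true ratio is 1.0. Let A be the AIN2+ found in Group 1, and q the share of these that also carry an untargeted type (tissue is typed for all 17 types). Then

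ratio = [(Tc + A)/(Uc + qA)] / (Tc/Uc) = (1 + A/Tc)/(1 + qA/Uc).

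This exceeds 1 whenever q < Uc/Tc. Since q is at most 1, it is enough that untargeted CIN2+ is no rarer than targeted CIN2+. With the infection mix that VII.A.2 assumes (25% targeted, 55% untargeted) as a stand-in, Uc/Tc = 2.2.

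**Step 3. Simple illustration (counts assumed).**
- Tc:Uc = 25:55, q = 0: A = 2, 5, 10 gives 27/25 = 1.08, 30/25 = 1.20, 35/25 = 1.40. With q = 0.5: 1.06, 1.15, 1.28.
- Tc:Uc = 5:55, q = 0: 1.40, 2.00, 3.00. With q = 0.5: 1.38, 1.91, 2.75.

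The bias grows as vaccination makes targeted CIN2+ rarer.

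**Step 4. The same from assumed risks.** All inputs are assumptions except 757 per group and 10% loss (VII.A.2), giving 681.3 women. Cervical persistence in the unvaccinated: HPV16/18 p = 0.05, untargeted u = 0.12. Lesion risks: targeted r = 0.2, untargeted s = 0.1. Co-infection q = 0.12. Vaccination multiplies p by RR = 0.5. Further, k is anal relative to cervical HPV16/18 persistence, d is anal relative to cervical lesion detection, and f is the share of women with AIN2+ who also have CIN2+ and count once.

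- Group 1 targeted: p·RR·r·[1 + k·d·(1−f)]. Untargeted: u·s + k·p·RR·q·s·d·(1−f). Group 3 has the cervical terms only.
- k = 1, d = 1, f = 0: expected counts 6.81 and 8.38 against 3.41 and 8.18; ratio (6.81/8.38)/(3.41/8.18) = 1.95.
- d = 0.5: 1.48. With f = 0.25 as well: 1.36. d = 0.25, f = 0: 1.24.
- Over k 0.25–2, q 0.12–0.5, RR 0.1–0.5, d 0.25–1, f 0–0.5: 1.03 to 2.97, always above 1.

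**Step 5. Co-infection rule.** Step 4 gives untargeted types their own lesion risk (q·s). If instead a co-infected AIN2+ counts under both type groups (q·r), the untargeted AIN2+ count is 681.3 × 0.025 × 0.12 × 0.2 = 0.41 rather than 0.20, and 1.95 becomes 1.90 (1.66 at q = 0.5). The plan states no rule.

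**Step 6. Sampling error, conditional on r and s.** SE of the log ratio = √(1/6.81 + 1/8.38 + 1/3.41 + 1/8.18) = 0.83, against a log bias of ln 1.95 = 0.67. Halving r and s leaves the ratio unchanged and raises the SE to 1.17; quartering them raises it to 1.65.

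**Step 7. Other pairs.** For Group 1 vs 2 both sides have the same trigger. With truth 0.50 and the base inputs the composite gives (0.0100/0.0123)/(0.0200/0.0126) = 0.51. At k = 2, q = 0.5 it is 0.5 × 0.0170/0.0145 = 0.59, or 0.5 × 0.022/0.017 = 0.65 under double counting. Group 3 vs 4 contains CIN2+ only.

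**Step 8. CIN2+ alone, Group 1 vs 3.** With A = 0 the ratio is 1.00. A residual remains if LEEP tissue from WLWH reveals CIN2+ that biopsy missed: 1 + e(1−b)/b, with b the share of CIN2+ found on biopsy and e the share of WLWH with persistent HPV16/18 who have LEEP. Assuming b = 0.75, e = 0.15: 1.05. For b 0.6–0.9 and e 0.05–0.3: 1.01 to 1.20.

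**The case against.** - **The target is inferred.** VII.A.1 names no pair and defines no composite, and the wording also allows CIN2+ alone. The infection contrast that is powered is Group 1 vs 2, where little changes. This stands in part: the analysis is unspecified rather than wrong as stated. But the preceding ratios include Group 1 vs 3, and nothing excludes AIN2+ from it.
- **VI.A might govern.** If anoscopy were offered regardless of HIV status, the asymmetry by HIV status would go, though entry by HPV16/18 alone would remain. The claim is therefore conditional on VI.G.2 and X.A.2, the more specific sections.
- **The inputs are generous.** VI.A calls precancer risk very low at these ages. The assumed p and u are close to 30% × 25% × 70% = 5.25% and 30% × 55% × 70% = 11.55% from VII.A.2, but those cover any site and, for targeted types, four types. This stands. It weakens any comparison of bias with standard error, but not the direction.

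Three stronger readings are tempting, and the documents support none of them. A reader might infer that an AIN2+-only ratio across HIV groups is planned; no section plans one, and it rests only on a reading of and/or. A reader might infer that the composite also fails for Group 1 vs 2; the shared trigger makes the base-case shift 0.50 to 0.51. A reader might infer that biopsy-only CIN2+ is required; the LEEP residual is small on assumed inputs, and dropping scarce events for it is a matter of preference.

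**Conclusion.** The concern holds as a minor point. With anoscopy as set out in VI.G.2 and X.A.2, a CIN2+ and/or AIN2+ ratio for vaccinated WLWH vs vaccinated HIV-negative women is biased upward and understates vaccine effectiveness in WLWH. The direction needs only q < Uc/Tc. The size cannot be determined from the documents: roughly 1.03 to 3 for a true ratio of 1.0 under the assumptions shown, depending on how co-infected lesions are counted. The bias may well be smaller than the sampling error, so it would not by itself be expected to produce a significant result.

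The Aim 1 infection outcomes are unaffected: all three sites are sampled at enrollment in every group, and the follow-up sampling rule does not depend on HIV status.

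**What to change.** Change the analysis wording in VII.A.1 only:

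1. Use CIN2+ alone for every WLWH vs HIV-negative disease contrast. Note that excision tissue from WLWH with persistent HPV16/18 may leave a small residual asymmetry.
2. Keep the CIN2+ and/or AIN2+ composite for Group 1 vs 2, and say how a lesion with both targeted and untargeted types is counted.
3. Report AIN2+ descriptively within WLWH, and state that it is ascertained only through the HPV16/18 anoscopy trigger.

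Two inconsistencies should be reconciled: VI.A with VI.G.2 and X.A.2 on who is offered anoscopy, and the exploratory label in VII.A.1 with the secondary label in VI.A and XI.

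The cost is a few sentences and the loss of a few AIN2+ events from the WLWH vs HIV-negative contrast. No change to who is examined or treated is proposed.

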Notably, the study groups of participants are fundamentally different populations (vs. a randomized control trial that would recruit from the same population and, as result of randomization, enroll similar, representative populations in each arm). Specifically, there are known differences in age (and therefore possible differences sexual behaviors) between Gardasil®-vaccinated vs. -unvaccinated WLWH, and possible differences in sexual behaviors between Gardasil®-vaccinated WLWH vs. HIV[-] women (since HIV infection predominately is sexually transmitted in this population). Therefore, we will use a relative measure of effectiveness to account for the differences in age and possible differences in exposure to HPV. We will use logistic regression to calculate the odds ratio (OR) of the point prevalence and the prevalence of persisting HPV infections of Gardasil®-targeted HPV types, individually (HPV6, 11, 16, or 18) and in aggregate (HPV6, 11, 16, and 18), vs. untargeted HPV genotypes for which there is no evidence of cross-protection, for each anatomic site individually (cervix, anus, OR oral cavity) and combined (cervix, anus, AND oral cavity). That is, we will compare the ratio between study groups of participants as follows:

$\frac{N_{HPV6/11/16/18}}{N_{HPV35/39/51/52/53/56/58/59/66/68}}$ [vaccinated WLWH] (Group 1)
 $\frac{N_{HPV6/11/16/18}}{N_{HPV35/39/51/52/53/56/58/59/66/68}}$ [unvaccinated WLWH] (Group 2)
 or

$\frac{N_{HPV6/11/16/18}}{N_{HPV35/39/51/52/53/56/58/59/66/68}}$ [vaccinated WLWH] (Group 1)
 $\frac{N_{HPV6/11/16/18}}{N_{HPV35/39/51/52/53/56/58/59/66/68}}$ [vaccinated HIV[-] women] (Group 3)

or

$\frac{N_{HPV6/11/16/18}}{N_{HPV35/39/51/52/53/56/58/59/66/68}}$ [vaccinated HIV[-] women] (Group 3)
 $\frac{N_{HPV6/11/16/18}}{N_{HPV35/39/51/52/53/56/58/59/66/68}}$ [unvaccinated HIV[-] women] (Group 4)

This will allow us to account for differences in HPV exposure, prevalence, and persistence due to differences in age (n.b., prevalence equals incidence * duration; prevalent infections at older ages tend to be more persistent ((108)) and sexual behaviors between groups. Additional logistic regression models may be used to adjust specifically on other factors, including age, number of doses, and sexual behaviors, to account for population differences between study groups.

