Sample size calculation relates to the relative effectiveness measure as discussed. Under above assumptions, a sample size of 757 vaccinated and 757 unvaccinated WLWH will provide $\geq 80\%$ power ($p=0.05$) to detect an OR of ≤ 0.5 for 6-12 month persistent HPV6/11/16/18 infections, relative to HPV35/39/51/52/53/56/58/59/66/68 (but not HPV31/33/45 because of possible cross protection), in Gardasil®-vaccinated vs. -unvaccinated WLWH. Consequently, because there will be more participants with a prevalent infection than 6-12 month persistent HPV infection (because there are no losses to follow-up or HPV viral clearance for which to account), there will

be $\geq 80\%$ power ($p=0.05$) to detect a OR of ≤ 0.75 in point prevalence of HPV6/11/16/18 infection relative to HPV35/39/51/52/53/56/58/59/66/68, in Gardasil®-vaccinated vs. - unvaccinated WLWH.

VII.B. Specific Aim 2

To quantify, and examine the determinants of, long-term antibody responses to, HPV vaccination.

VII.B.1. Analyses.

Geometric mean titers (GMT) and seropositivity (seroconversion) will be compared between 1) HPV-vaccinated WLWH and HPV-vaccinated HIV[-] women, overall and stratified on the number of vaccine doses, 2) HPV-vaccinated and unvaccinated WLWH, overall and by the number of doses received by the HPV-vaccinated WLWH, and 3) three vs. two doses for HPV-vaccinated WLWH and 4) HPV-vaccinated and unvaccinated HIV[-] women, overall and by the number of doses received by the HPV-vaccinated HIV[-] women.

Differences in GMT and seropositivity will be tested for statistical significance using the Mann-Whitney and Fisher's exact tests, respectively. ANOVA and logistic regression models will be used to adjust for/assess the association of other factors (e.g., age at vaccination, age at enrollment into the study, number of doses, HIV status [positive vs. negative and current antiretroviral therapy, CD4 counts, and HIV viral load] and history [e.g., CD4 nadir], and detection of HPV genotypes, etc.) with GMT and seropositivity, respectively.

Among vaccinated and unvaccinated HPV seropositive WLWH, the association between HPV antibody titer and presumed route of HIV acquisition (either maternal to child or behavioral) will be examined.

VII.B.2 Sample Size/Power to compare Gardasil®-vaccinated WLWH vs. Gardasil®-vaccinated HIV[-] women.

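### Section VII.A.2: the claim of at least 80% power for an odds ratio of 0.75 on HPV point prevalence is wrong (about 22–25% two-sided at the plan's own inputs), and it does not follow from the persistence claim

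*Combined protocol and SAP*

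**What the plan says.** Section VII.A.1 makes the Aim 1 measure relative: targeted types (HPV6/11/16/18) against untargeted types without cross-protection, compared between groups. "We will use logistic regression to calculate the odds ratio (OR) of the point prevalence and the prevalence of persisting HPV infections" is the stated method. Section VII.A.2 ties power to it: "Sample size calculation relates to the relative effectiveness measure as discussed".

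The inputs in VII.A.2 are a baseline prevalence of at least 30% at any site, of which "25% of which will be Gardasil®-target HPV types and 55% will be untargeted HPV types"; 10% loss to follow-up; and "at least 70% of HPV infections persist for 6-12 months". On prevalence the text adds that "we conservatively used 30% to ensure adequate statistical power", so 30% is the design value.

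With 757 per group the section claims at least 80% power (p=0.05) "to detect an OR of ≤ 0.5 for 6-12 month persistent HPV6/11/16/18 infections". It continues: "Consequently, because there will be more participants with a prevalent infection than 6-12 month persistent HPV infection", and concludes that there is also at least 80% power "to detect a OR of ≤ 0.75 in point prevalence of HPV6/11/16/18 infection". It does not give the formula, the sidedness, the number of infections per woman, or the group that the 25/55 split describes.

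**The concern.** An OR of 0.75 is a much smaller effect than 0.5. On the log scale it is ln 0.75 = −0.288 against ln 0.5 = −0.693, a factor of 2.4, and required information grows roughly with the square of that. Moving from persistence to prevalence recovers only the infections lost to follow-up or cleared. It is hard to see how that pays for so large a change in effect size.

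These are the only power statements for Aim 1. If the prevalence statement stands, a non-significant prevalence comparison could be read as adequately powered evidence against a moderate effect when it is not.

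**Working it through.** **Inputs (VII.A.2).** N = 757 per group; prevalence 0.30; targeted 0.25, untargeted 0.55, so 0.80 of infections are informative; retained and persistent 0.9 × 0.7 = 0.63; alpha 0.05. My assumption: one infection per positive woman.

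- Prevalent informative infections per group: 757 × 0.30 × 0.80 = 181.7 (56.8 targeted, 124.9 untargeted).
- Persistent: 181.7 × 0.63 = 114.5 (35.8 targeted, 78.7 untargeted).
- Targeted share: 25/80 = 0.3125; odds 25/55 = 0.4545.

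**Trying to reproduce the plan's 80%.** The closest match for persistence reads 0.5 as a ratio of targeted shares, 0.3125 against 0.15625. The pooled z test then has 80.1% power at 757 and needs about 755 per group. But that contrast is an OR of (0.15625/0.84375)/0.4545 = 0.41, and the plan says OR. The same reading of 0.75 on prevalence gives 39% two-sided and 51% one-sided. How 757 was in fact derived is not stated.

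**Power formulas.** Pooled z: Φ[(|p1−p2| − z·√(2p̄(1−p̄)/n)) / √((p1(1−p1)+p2(1−p2))/n)]. Wald on the log OR: Φ[|ln OR|/√(1/a+1/b+1/c+1/d) − z]. Two-sided z = 1.96.

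*Prevalence, OR 0.75, split on the unvaccinated group.* Vaccinated odds 0.75 × 0.4545 = 0.3409, so p2 = 0.2542.
- Equal informative totals: (0.0583 − 1.96 × 0.0473)/0.0472 = −0.73, power 23%.
- Equal untargeted counts (56.8/124.9 against 42.6/124.9): 0.2877/0.2390 − 1.96 = −0.76, power 22%.

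*Persistence, OR 0.5, same split.* p2 = 0.1852.
- Equal totals: (0.1273 − 1.96 × 0.0572)/0.0565 = 0.27, power 61%.
- Equal untargeted counts (35.8/78.7 against 17.9/78.7): 0.6931/0.3305 − 1.96 = 0.14, power 55%.

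**By the group the split describes** (first row spans both layouts; the others use equal totals):

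| Split describes | Prevalence, OR 0.75: two-sided (one-sided) | Persistence, OR 0.5: two-sided (one-sided) |
|---|---|---|
| Unvaccinated | 22–23% (33–34%) | 55–61% (67–72%) |
| Average of groups | 24% (35%) | 67% (78%) |
| Vaccinated | 25% (37%) | 72% (82%) |

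One further layout falls just outside these ranges. With the split on the vaccinated group and untargeted counts held equal, the prevalence cells are 75.7/124.9 against 56.8/124.9: 0.2877/0.2164 − 1.96 = −0.63, power 26%. The persistence cells are 71.5/78.7 against 35.8/78.7: 0.6931/0.2595 − 1.96 = 0.71, power 76%. No conclusion changes.

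**What would restore 80% two-sided.**
- Prevalence, OR 0.75: about 4.6–5.4 independent infections per positive woman. With the split on the unvaccinated group and one infection each, even 100% prevalence gives only 59–61%.
- Persistence, OR 0.5: about 1.2–1.8 independent infections per positive woman, or correspondingly higher prevalence.

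**The inference from persistence to prevalence.** Informative infections needed per group (split on the unvaccinated group, equal totals): about 938 for OR 0.75 and 180 for OR 0.5, a ratio of 5.2. Available gain: 1/0.63 = 1.59. Suppose persistence has exactly 80% power at OR 0.5. Prevalence then supplies 180/0.63 = 286 infections per group, which gives 34% power for OR 0.75. Across the readings in the table the range is about 30–36% two-sided, or 35–41% if sized and tested one-sided throughout. Such a design detects about 0.58–0.59 on prevalence; as a quick check, exp(ln 0.5 × √0.63) = 0.577. The number of infections per woman cancels if it is the same for both endpoints.

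**The case against.** The best defence is that one infection per positive woman is not in the plan. VII.A.1 counts type-specific infections, 17 types are tested at three sites, and the 30% is described as a floor. It rests on high-risk cervical infection alone, whereas the endpoint adds anal and oral sites and HPV6/11. The 25/55 split is not assigned to a group, and sidedness is not given.

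For persistence this defence largely stands. A reader might infer that the OR 0.5 claim is also an error and that the study is underpowered for its main endpoint. The documents do not support that. About 80% returns one-sided with the split on the vaccinated group (82%), with a modest number of infections per woman, with higher prevalence, or on the ratio-of-shares reading. What can be said is that the claim cannot be reproduced two-sided at one infection per positive woman.

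For prevalence the defence fails. The number of infections needed appears nowhere in the documents. With the split on the unvaccinated group, a number large enough to give 80% there would put persistence power at OR 0.5 above 99%. The only single-infection route found to 80% treats all 757 women as informative and tests one-sided (81%), which contradicts 30% prevalence.

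Two further points limit the consequence. VII.A.2 ties 757 to persistence, and IX.E calls 6–12 month retention the basis of the main endpoint, so the prevalence statement did not set the sample size. VII.A.1 also plans 95% confidence intervals, so precision would be visible when results are read. Neither point makes the power statement true.

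**Conclusion.** The statement of at least 80% power for an OR of 0.75 on point prevalence is wrong as written. At the plan's inputs and one infection per positive woman it is about 22–25% two-sided (33–37% one-sided), under every assignment of the 25/55 split. The step from persistence to prevalence is invalid for any number of infections per woman common to both endpoints: 1.6 times as many infections cannot cover a need of about five times as many.

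The persistence statement is conditional. Two-sided with one infection per positive woman it is 55–61%, 67% or 72%, according to whether the split describes the unvaccinated group, the average or the vaccinated group. It should be specified and re-derived. It has not been shown to be false, and nothing here shows that 757 per group is too few. All figures are large-sample approximations and treat infections as independent.

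**What to change.** Keep enrolment, endpoints and analysis, and rewrite the power paragraph in VII.A.2:

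- Delete the inference from persistence to prevalence and the 0.75 figure. Replace them with the detectable prevalence OR from the actual calculation. At the stated inputs and one infection per positive woman this is about 0.47–0.54 with 80% two-sided power. If the persistence claim holds at exactly 80%, it is about 0.58–0.59.
- Re-derive the persistence figure. State whether N counts women or infections, the infections assumed per woman with an allowance for within-woman correlation, the group that the 25/55 split describes, the test and its sidedness. Show targeted and untargeted counts per group.
- If the calculation is two-sided with one infection per positive woman, restate the detectable persistence OR as about 0.36–0.47, depending on the split. If 0.5 was meant as a ratio of targeted shares, say so and give the equivalent OR of about 0.41.

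The cost is one paragraph and less favourable stated figures. No participants are added.
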